If UFC > ULN, the site will contact the patient to plan an interim escalation dose visit 7 days after the regular visit (on Day 21). At the interim visit, the patient will take the first escalated dose at the site, and remain for 1.5 hours in order to have a 12-lead Safety ECG. This ECG must be read on site by a qualified physician (e.g., the investigator, or another qualified physician such as a consulting cardiologist), who will decide whether or not there is a “notable abnormality”. Notable abnormality is defined as QTcF > 480msec with acute cardiac risk, QTcF > 500msec, or increase in QTcF > 60msec from baseline QTcF from the pre-dose ECG taken on the day of the first study drug administration (Day 1). If there is no notable abnormality, then the patient will be sent home to continue the higher dose until the next visit on the current schedule. If there is a “notable abnormality,” then a cardiology consult should be called, and the Novartis “Medical Monitor” for this trial notified of the event.

This schedule of events will continue every 2 weeks (i.e. Day 28, 42, 56) with potential interim dose escalation visits (on Days 35, 49, 63) during the dose escalation period, with the dose of LCI699 increasing according to [Figure 3-1](#). If at any time, the patients UFC is < ULN, dose escalation will be halted and the patient will remain on the current, efficacious dose through the rest of the dose escalation period (Week 10), and if UFC remains normal, continue until Week 22. Monitoring of UFC responses will continue every 2 weeks to allow additional dose adjustments if necessary. Accordingly, only a predose PK sample will be required for patients that remain on the efficacious dose. If at any time the patient experiences side effects which are either intolerable or meet dose adjustment criteria, the prescribed dose will be adjusted as outlined in [Section 5.5.4](#).

Between days 66-69, patients will perform three 24-hour urine collections. Patients will bring in their urine collection bottles to the site on Day 70 \pm 2 days. A pre-dose PK sample only (12 hr post previous PM dose) will be collected for patients on their previous maintained dose (<30 mg bid). Pre-dose (12 hr post previous PM dose), 1, 1.5, 2, 4 and 6 hour PK samples will be collected for patients receiving 30 mg bid. Patients will undergo safety/PD assessments at the site on Day 70 \pm 2 days.

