5.5.3.1 Instructions for prescribing and taking study treatment

Patients will self-administer LCI699 p.o. b.i.d. in the morning and evening regardless of when they have eaten.

The investigator should promote compliance by instructing the patient to take the study drug exactly as prescribed and by stating that compliance is necessary for the patient's safety and the validity of the study. The patient should be instructed to contact the investigator if he/she is unable for any reason to take the study drug as prescribed.

The patients will also be instructed to bring back used and unused medication at selected time-points for drug accountability checking.

Patients must be instructed not to chew the medication, but to swallow it whole. All dosages prescribed and dispensed to the patient and all dose changes during the study must be recorded on the Dosage Administration Record eCRF.

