5.5.11 Discontinuation of study treatment

Patients may voluntarily discontinue from the study treatment for any reason at any time. If a patient decides to discontinue from the study treatment, the investigator should make a reasonable effort (e.g. telephone, email, letter) to determine the primary reason for this decision and record this information in the patient's chart and on the appropriate CRF pages. They may be considered withdrawn if they state an intention to withdraw, fail to return for visits, or become lost to follow-up for any other reason.

The investigator should discontinue study treatment for a given patient if he/she believes that continuation would be detrimental to the patient's well-being.

Study treatment must be discontinued under the following circumstances and according to Investigator discretion:

- Withdrawal of informed consent.
- Emergence of the following adverse events (compound specific):
 - hypertension defined as office mean sitting systolic BP > 180 mmHg or mean sitting diastolic BP > 110 mmHg (confirmed and persistent*).
- Any of the following laboratory abnormalities:
 - hyperkalemia (serum potassium > 5.5 mmol/L; confirmed and persistent*).
 - hypokalemia (serum potassium < 3.5 mmol/L; confirmed and persistent*).
 - hyponatremia (serum sodium < 130 mmol/L; confirmed and persistent*).
- QTcF > 500 msec, if confirmed by a cardiologist (see [Section 6.6.5](#)).
- QTcF > 480 msec, if the investigator determines it is no longer safe for the patient to continue in the study, based on ECGs, cardiac examination, and recommendation from a cardiologist (see [Section 6.6.5](#)).
- Pregnancy.
- Use of any other therapy for Cushing's disease.
- Any other protocol deviation that results in a significant risk to the patient's safety.

* Persistent is defined as unresolved with LCI699 dose or other concomitant medication changes

Patients who discontinue study treatment should NOT be considered withdrawn from the study. They should return for the assessments indicated in [Section 6](#). If they fail to return to return for these assessments for unknown reasons, reasonable effort (e.g. telephone, email, letter) should be made to contact them as specified in [Section 5.5.13](#).

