6.6.5 Electrocardiogram (ECG)

Cardiac monitoring will include 12-lead Safety ECGs, which are the primary assessment of safety at study visits, and 24-hour continuous 12-lead Holter recordings, which provide large amounts of additional ECG data with central reading, but are not intended to provide real-time assessment of cardiac intervals and cardiac rhythm.

Twenty-four hour continuous 12-lead Holter recording with central reading of data are done on each patient according to the [Assessment schedules](#).

Twelve-lead safety ECGs are collected at the study sites according to the [Assessment schedules](#). At each visit when a study drug dose is administered, the safety ECG should be collected at 1.5 hours post-dose (approximately at the time of C_{max}). If the patient chooses to enroll in long term extension-1 and long term extension-2 studies, 12-lead safety ECGs will also be done according to the [Assessment schedules](#), and the timing will also be 1.5 hours post-dose if study drug is administered.

Twelve-lead safety ECGs are collected at the study site using local ECG equipment. This ECG must be read on site by a qualified physician (e.g., the investigator, or another qualified physician such as a consulting cardiologist) at the time they are collected and documented on the ECG section of the CRF / eCRF.

Each 12-lead Safety ECG tracing should be labeled with the:

- study number
- patient initials
- patient number
- date and time

and kept in the source documents at the study site. The clock on the ECG machine should be synchronized with the central clock on a daily basis.

The eCRF will contain:

- date and time of ECG
- heart rate
- PR interval
- QT and QTc interval

- QRS duration

The Fridericia QT formula (QTcF) to correct for variations in heart rate should be used for clinical decisions ([Fridericia 1920](#)).

The purpose of the safety ECG is to identify patients with clinically significant (“notable”) ECG abnormalities. On the day of the first study drug administration (day 1), the pre-dose ECG must be done in triplicate. The mean of the QTcF from these 3 tracings is used as the baseline QTcF to be compared with the 1.5 hour post-dose ECG on Day 1 only.

Only ECGs with clinically significant (“notable”) abnormalities should be reported on the ECG tracing. A “notable abnormality” is defined as:

- Day 1 only: an increase in QTcF > 30msec at 1.5 hours post-dose, compared to the mean pre-dose baseline QTcF from the same day

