- QTcF > 480msec with acute cardiovascular risk, as assessed by a consulting cardiologist
- Any QTcF > 500msec, confirmed by a consulting cardiologist

Notable ECG abnormalities should be recorded on the Adverse Events e(CRF) page. The overall interpretation will be collected with a Yes/No statement to confirm if any clinically significant abnormalities are present which need to be specified further.

For any ECGs with patient safety concerns, two additional 12-lead ECGs should be performed to confirm the safety finding. If there is a notable abnormality, then a cardiology consult should be called, and the Novartis Medical Monitor for this trial notified of the event.

ECGs must be recorded after 10 minutes rest in the supine position to ensure a stable baseline. The preferred sequence of cardiovascular data collection during study visits is ECG collection first, followed by vital signs, and then blood sampling for LCI699 pharmacokinetic (PK) assessment ([Figure 6-1](#)).

Figure 6-1 Sequence of cardiovascular data collection

Original ECG tracings, appropriately signed, will be archived at study site.

QT prolongation monitoring

On the day of the first administration of LCI699 (day 1), the pre-dose baseline ECG must be done in triplicate. The mean of the QTcF values from these three ECG tracings is used to determine the mean baseline QTcF for that day only. If the safety ECG (1.5 hours post-first dose of LCI) shows an increase in QTcF > 30ms from the mean baseline value, or the QTcF is > 480ms, then the patient should be discontinued from study drug. Any ECG in doubt

should be reviewed promptly by a consulting cardiologist before discontinuing the patient from LCI699 therapy.

If at any follow up visit, a QTcF > 500msec is observed on the 1.5 hour post-dose safety ECG, then triplicate ECGs, each 2-3 minutes apart, need to be taken after the initial ECG. The mean QTcF from the triplicate ECGs will be determined. If the mean QTcF is > 500msec, the patient has to interrupt study treatment while an urgent cardiology consultation is obtained to re-evaluate the ECG and perform a clinical consultation. If immediate treatment is required for patient safety, this should be initiated at the study site without delay and without waiting for confirmation by a cardiologist.

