If the cardiologist confirms a mean QTcF > 500msec, the patient has to discontinue according to the discontinuation procedure described in [Section 5.5.9](#). The patient must remain under observation until the QTcF is < 480msec and serum electrolytes, calcium, and magnesium are measured and the results normal. This observation may be done at the site, in an Emergency Room, or a cardiology clinic, as appropriate and depending upon local resources.

Otherwise, and if the cardiologist confirms, that at least one ECG shows a QTcF > 480msec, the cardiac assessments described for a confirmed QTcF > 480msec need to be followed.

[figure not shown]
If at any follow up visit a $480\text{msec} < \text{QTcF} \leq 500\text{msec}$ is observed on the 1.5 hour post-dose safety ECG, the following steps need to be taken (described in [Figure 6-2](#)):

The patient has to interrupt study treatment while an urgent cardiology consultation is obtained to re-evaluate the ECG. If immediate treatment is required for patient safety this should be initiated at the study site without delay and without waiting for confirmation by a cardiologist.

- If a QTcF > 480msec is NOT confirmed, no further action needs to be taken;
- If a QTcF > 480msec is confirmed, a cardiologist must perform a thorough clinical evaluation to assess the patient for acute cardiovascular risk, and for possible underlying heart disease that needs additional evaluation and management.
 - a. If based upon the assessment by the cardiologist, the investigator considers that there is an acute cardiovascular safety risk and that the subject should not continue with study medication, the subject needs to be discontinued immediately (discontinuation criteria described in [Section 5.5.9](#)).
 - b. If based upon the assessment by the cardiologist, the investigator considers that there is not an acute cardiovascular safety risk, the subject can continue to receive study medication.

The patient must remain under observation until the QTcF is < 480msec and serum electrolytes, calcium, and magnesium are measured and the results are normal. This observation may be done at the site, in an Emergency Room, or a cardiology clinic, as appropriate and depending upon local resources. The results of the ECGs, cardiac examination and the recommendation by the cardiologist must be evaluated by the investigator to determine whether the subject should continue in the trial or not.

Figure 6-2 QT Prolongation Monitoring Flow Chart

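### Section 6.6.5 states no treatment hold when a first follow-up QTcF above 500 ms is followed by a triplicate mean of 500 ms or less, although a single reading above 480 and up to 500 ms requires one at once

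*Protocol*

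**What the plan says.** Protocol Section 6.6.5 (QT prolongation monitoring) sets two follow-up pathways. Both start from the safety ECG taken after dosing: "At each visit when a study drug dose is administered, the safety ECG should be collected at 1.5 hours post-dose".

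- **First reading above 500 ms.** Three further ECGs are taken 2 to 3 minutes apart. The hold depends on their mean: "If the mean QTcF is > 500msec, the patient has to interrupt study treatment while an urgent cardiology consultation is obtained". A mean above 500 ms that the cardiologist confirms leads to discontinuation. A fallback sentence follows: "Otherwise, and if the cardiologist confirms, that at least one ECG shows a QTcF > 480msec". It sends the patient to the assessments laid down for a confirmed value above 480 ms.
- **First reading above 480 and up to 500 ms.** No repeat is needed first: "The patient has to interrupt study treatment while an urgent cardiology consultation is obtained to re-evaluate the ECG". If the value is confirmed, a cardiologist evaluates the patient, the investigator decides whether treatment continues, and observation lasts until QTcF is below 480 ms with normal electrolytes.

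Three other rules bear on the same readings:

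- Section 5.5.11 lists two discontinuation grounds: "QTcF > 500 msec, if confirmed by a cardiologist" and "QTcF > 480 msec, if the investigator determines it is no longer safe for the patient to continue in the study".
- Section 3.1 covers interim dose-escalation visits: "Notable abnormality is defined as QTcF > 480msec with acute cardiac risk, QTcF > 500msec, or increase in QTcF > 60msec". There the patient goes home on the higher dose only if no such abnormality is found; otherwise a cardiology consult is called.
- Section 6.6.5 also calls a consult, and notifies the medical monitor, for any notable abnormality. Its definition includes a QTcF above 500 ms, but only once a consulting cardiologist has confirmed it.

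**The concern.** A stopping rule should not become less protective as the reading gets worse. Here a single 490 ms tracing suspends treatment at once. A 510 ms tracing whose repeats average 495 ms suspends nothing in the visible text. The fallback sentence does not fill the gap: it brings in the steps that follow confirmation of a value above 480 ms, and in the 480 ms pathway the hold comes before confirmation.

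What is at stake is the next dose. If the cardiologist has not decided by then, the text does not tell the site whether to give it, and sites may act differently. This is a point of safety consistency, not of estimation.

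**Working it through.** The plan gives no figure to reproduce, so the check traces the rules. All QTcF readings below are illustrative.

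**1. Stated hold by first reading and repeats**

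| First reading (ms) | Triplicate (ms) | Mean (ms) | Hold stated in 6.6.5? |
|---|---|---|---|
| 481 or 490 | not required | n/a | Yes, at once, with urgent cardiology |
| 505 | any set with mean 505 | 505 | Yes, with urgent cardiology |
| 505 | 498, 499, 497 | 1494/3 = 498 | None stated |
| 510 | 505, 502, 478 | 1485/3 = 495 | None stated |

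In the third row every repeat lies above 480 and up to 500 ms. A site could reasonably treat that as entering the 480 ms pathway, although its trigger is the 1.5-hour safety ECG and not the repeats. In the fourth row no tracing lies in that band and 3 of 4 exceed 500 ms, so that reading is not available.

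**2. Do other rules supply the hold?**

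- Section 5.5.11: both grounds act only after a cardiologist's confirmation or the investigator's determination. No hold is ordered while that is pending.
- Section 6.6.5, notable abnormality: the consult depends on a cardiologist's confirmation, and no hold is stated.
- Section 3.1, interim visits: QTcF above 500 ms is notable without confirmation, so continuing the escalated dose is not authorised. No explicit hold is stated, and the rule covers interim visits only.
- Fallback sentence: it cannot operate without a cardiologist, so review is implied, but neither urgency nor a hold is stated.

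Cardiology involvement is therefore partly covered. The interim hold is not.

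**3. Time to the next dose.** Section 5.5.3.1: "Patients will self-administer LCI699 p.o. b.i.d. in the morning and evening". Section 3.1 places the pre-dose sample 12 hours after the evening dose. With the ECG at 1.5 hours, 12 − 1.5 = 10.5 hours remain.

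**4. Scope under the current version**

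- Amendment 9: 10 patients ongoing on 03 May 2018; latest end 31 December 2019. That is 607 days, or about 19.9 months.
- Visit interval: all core completers had finished by 01 March 2014 (Amendment 6). Day 490 is 490 − 154 = 336 days later, so by about 31 January 2015. Adding the 18 months of three-monthly visits gives about the end of July 2016. Visits were six-monthly by May 2018.
- 19.9/6 = 3.3, so 3 or 4 scheduled post-dose ECGs per patient. 10 × 3 to 10 × 4 = 30 to 40 in all.
- This is an upper range, because patients may leave earlier for the roll-over study. End-of-treatment visits are not counted, since no dosing is marked there. The core visits were already over.

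**The case against.** **Figure 6-2.** The section has its own flow chart, which is not visible here, so the documents as available cannot show that the plan lacks the step. This stands as a condition on the whole point. Text and figure should still agree.

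**Triplicates as the immediate action.** Above 500 ms the protocol verifies with three tracings; in the lower band, where no repeat is ordered, the hold may stand in for verification. That explains deferring the hold for the few minutes the repeats take. It does not explain dropping it when the repeats return at a level that would itself require a hold as a first reading.

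**Narrowness.** If repeats between 480 and 500 ms are taken to enter the lower pathway, two cases remain. Either all repeats are at or below 480 ms and the first reading looks spurious, or tracings minutes apart straddle the band by more than 20 ms. In the 510 ms example, confirmed tracings above 500 ms would be a discontinuation ground under Section 5.5.11, which is stronger than a hold. An on-site physician reads each ECG, and the investigator should already stop treatment judged detrimental. All of this stands and limits the point to the interval before the cardiologist decides.

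**Thorough QT study.** Section 3.5 reports a reassuring predicted mean effect at 2 to 30 mg twice daily. That gives no support for urgency, but a mean effect does not exclude individual outliers, and the current version keeps the individual stopping rules.

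**Stronger readings a reader might infer.** One is that such a patient receives no cardiology review or may simply carry on; the rules in Sections 3.1, 5.5.11 and 6.6.5 contradict that. Another is that every first reading above 500 ms needs a hold whatever the repeats show; where all repeats are at or below 480 ms, the comparison with the lower pathway does not carry that far.

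**Conclusion.** The point holds in a limited form. In the visible text, a follow-up safety ECG above 500 ms with a triplicate mean of 500 ms or less carries no stated hold, while a single reading above 480 and up to 500 ms does. The gap is confined to the interim hold before the cardiologist's decision. After confirmation above 480 ms the patient is properly evaluated and observed.

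The conclusion assumes that Figure 6-2 does not already state the hold and that the repeats do not count as the 1.5-hour safety ECG. The practical consequence further assumes a 12-hour dosing interval. The branch should be rare, but the documents give no basis for a rate and none is claimed. Nothing here bears on the trial's QT conclusion, and inferring that it does would go beyond the documents. The change is worth making but is not critical; confidence is medium.

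**What to change.** Add one sentence to Section 6.6.5: after a first follow-up QTcF above 500 ms with a triplicate mean of 500 ms or less, treatment is held pending an urgent cardiology re-read whenever the triplicate mean or any repeat tracing exceeds 480 ms. A mean above 480 ms implies at least one such repeat, so the working test is simply any repeat above 480 ms. The mean then only decides which pathway applies. If all repeats are at or below 480 ms, the present fallback route can remain.

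Align Figure 6-2 with one arrow if needed; if it already shows the hold, carry it into the text.

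Cost: one sentence, under the written amendment that Section 11.1 requires, and no additional ECGs. Each event needs one urgent cardiology review, and if that is done within about 10.5 hours no dose need be missed. The downside is an occasional short interruption or consult for a reading that proves spurious.

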6.6.6 Pituitary MRI

Pituitary MRI scanning with gadolinium enhancement will be performed at visits according to the [Assessment schedules](#). These will be assessed locally to determine tumor volume and longest diameter and recorded in the eCRF. If MRI intravenous contrast is contraindicated for a patient, a non-contrast MRI scan should be performed. If MRI cannot be performed at all then a CT (with i.v. contrast if not contraindicated) may be performed. Digital copies of all imaging should be kept on site in the event Novartis requests their transfer for review/adjudication. Please see the study imaging manual for further information.

6.6.7 Pregnancy

Pregnancy tests are required of all female patients regardless of reported reproductive/menopausal status.

Serum pregnancy tests will be performed at screening, baseline and End of Study visit. Urine or serum pregnancy testing will be performed as indicated in the [Assessment schedule](#).

If a urine pregnancy test is performed and is found to be positive, this will require immediate interruption of study drug until serum β -hCG is performed and found to be negative. If positive, the patient must be discontinued from the trial.

When performed at screening and baseline, the result of this test must be received before the patient may be dosed.

6.6.8 Meal record

Not applicable.

6.7 Pharmacokinetics

6.7.1 Pharmacokinetics

The PK parameters of LCI699 to be assessed are listed in [Table 6-1](#). Visit schedules for LCI699 PK blood collection are shown in [Table 6-2](#).

If data allows, $C_{trough,ss}$ will be utilized as concentration at 12 h post-dose for the calculation of $AUC_{0-12,ss}$ and $T_{1/2,ss}$. This is based on the PK principle that at steady state, C_{trough} is assumed to be the same at the beginning and end of the dose interval, in this case 12 h.

Table 6-1 Non-compartmental pharmacokinetic parameters for LCI699

$C_{max,ss}$	The maximum plasma concentration at steady state. The unit is ng/mL.
$T_{max,ss}$	The time to reach the maximum plasma concentration at steady state. The unit is hr.
$AUC_{0-6hr,ss}$	The AUC from time zero to 6 hours post dose at steady state. The unit is hr*ng/mL.
$AUC_{0-12hr,ss}$	The AUC from time zero to 12 hours post dose at steady state, calculated by using the pre-dose concentration ($C_{trough,ss}$) as the 12 hr concentration, assuming steady-state has been reached. The unit is hr*ng/mL.
$T_{1/2,ss}$	The elimination terminal half-life at steady-state. The unit is hr.
$C_{trough,ss}$	The pre-dose concentration at steady-state. The unit is ng/mL.

